Step 8:	For CYP completing the interventions in the first 18 months of the trial, follow-up SDQ and SRDS questionnaires will be collected, 6 months after the completion of the interventions.
Step 9:	One month before the trial ends, police administrative data are collected from the Police National Computer via GMP.

Table 2: Trial design

Trial design, including number of arms		Two-arm Randomised Controlled Trial
Unit of randomisation		Individual CYP
Stratification variables (if applicable)		N/A
Primary outcome	variable	The primary outcome of interest in this study will be contact with the police, as perpetrators, victims or missing person episodes.

	
measure (instrument, scale, source)
	
Police contact data will be taken from Greater Manchester Police administrative records. Police contact data is a count variable starting at 0. These data will be collected one month before the trial ends. Data will be taken for a period 1 year prior to the recruitment date. Every CYP will have a 3-month follow-up period after completion of the intervention.

Secondary outcome(s)
	
variable(s)
	
The secondary outcomes will be the CYP's emotional and behavioural difficulties and self-reported delinquency. Emotional and behavioural difficulties are measured by the following three variables:
 
 1) Internalizing score 2) Externalizing score 3) Total difficulties 
Self-reported delinquency is measured by:
 
 4) Variety of delinquency 5) Volume of delinquency
	
measure(s) (instrument, scale, source)
	
The first three scores are measured with the Strengths and Difficulties Questionnaire (SDQ). The remaining two scores (4 & 5) are measured with the Self-Reported Delinquency Scale (SRDS).
 
The SDQ and SRDS are completed by CYP at the point of consent, the end of the interventions and 6 months after the end of the interventions as a follow-up (for CYP who start the interventions in the first 18 months of the trial).
 
For the SDQ CYP are asked to recall over the past 6 months, a period defined in the measure. For the SRDS, CYP are asked to recall over the past 3 months, this was a period defined for this study, in consultation with Remedi.
 
In the pilot study 73% of CYP consented into the interventions completed the initial questionnaires,

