The intervention will be offered to CYP aged 10-17 who have committed a violent offence or have displayed violent behaviour identified by the police and youth justice services. The diagram below provides a summary of the stages of the intervention and anticipated numbers of CYP participating in the intervention.

Figure 5. Intervention and control group process summary

The following inclusion and exclusion criteria will be used. Referrals will consist of any young person (10-17) in receipt of a police outcome, up to and including an out of court

disposal (at any level⁷) that has committed a violent offence in Greater Manchester. Once referred to Remedi, CYP must provide written, informed consent (or assent if relevant) before any study procedures occur. The same process would apply for parents/carers of CYP. CYP who are unable to take part or who fail to engage with the intervention would be excluded from the study. In addition, CYP should not participate in other youth support programmes at the same time as the RM or RC intervention.

We will request both CYP assent and their parents/carers' consent in line with Remedi's processes to involve CYP and their carers in the consenting process. The only exception to this would be 17-year-olds living independently, of who there are expected to be few.

Trained Remedi mentors will introduce the trial to CYP who will explain the main aspects of the mentoring programme. CYP and their parents/carers will also receive information sheets. Mentors will discuss the trial with CYP in light of the information provided in the information sheets. CYP and their parents/carers will then be able to have an informed discussion with the mentor. Mentors will obtain written assent (and consent where applicable) from CYP and written consent from parents/carers willing to participate in the trial.

Police and Youth Justice services will identify and refer CYP cases satisfying the above criteria to Remedi. The mentoring meetings, which include data collection, will take place in Greater Manchester, in the buildings of local authorities and the Greater Manchester Police. The questionnaire data will be transferred to the Remedi case management system by the mentors. The police administrative data will be collected by appropriately authorised Remedi staff that will be given access to a police computer.

Sample size calculations

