The planned number of the trial participants is 352 CYP in its two years of implementation, 176 in the RM group and 176 in the RC group. The sample size is such that the trial is sufficiently powered to detect a Cohen's d of at least 0.3. At the same time, the sample size is in line with the recruitment capacity, funder guidelines and the previous literature, see e.g. O'Connor and Waddell (2015) for a review. The mean effect sizes found in that paper for youth violence interventions range between 0.19-0.4. The calculations are done in Matlab based on Rosner (2011).

Table 3: Sample size calculations

⁷ Community resolution, Youth caution, Youth conditional caution, plus CYP who have been in contact with the police for a violent offence, but no further action has been taken.

		PARAMETER
Minimum Detectable Effect Size (MDES)		0.3
Alpha		0.05
Power		0.8
One-sided or two-sided?		Two-sided
Number of participants	Intervention	176
	Control	176
	Total	352

The above calculations report the sample size for the whole study over a two-year period.

Outcome measures

Primary outcome

The primary outcome of interest is the number of contacts of the CYP with the police, as perpetrators, victims or missing person episodes⁸. This will be measured using police administrative data from Greater Manchester Police (COGNOS system). Data will be taken for a period 1 year prior to the recruitment date and 3 months following the end of the interventions for each CYP. Police contact data is a discrete variable starting at 0.

This is a broad definition and was chosen because the CYP being referred to the RM or RC interventions were expected to have only had limited contact with the police. As a result, relying only on subsequent arrests and proven offending risked minimising their further contact with the police.

Secondary outcomes

The secondary outcomes will be the CYP's emotional and behavioural difficulties (as measured by the Strengths and Difficulties Questionnaire, SDQ) and self-reported delinquency (as measured by the Self-Report Delinquency Scale, SRDS).⁹ CYP will complete these at the point of consent, at the end of the interventions and 6 months

⁸ In cases where a CYP was arrested and rearrested for the same offence, we would create a rule that as this relates to the same offence, this would count as one arrest.

⁹ Full questionnaires for both the SDQ and SRDS are provided at Appendix 2.

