Quantitative	Provision of administrative data by Greater Manchester Police	Administrative data on intervention and control group contact with the police (as perpetrators, victims or missing person episodes) (N=352)	Poisson regression, Negative Binomial regression, t-test, Cohen's d.	1. Establish whether RM is more effective than RC in terms of contact with the police.
	SRDS Questionnaires	RM (N=176) RC (N=176)	Linear regression, t-test, Cohen's d.	1. Establish whether RM is more effective than RC in terms of contact with the police.
	SDQ Questionnaires	RM (N=176) RC (N=176)	Linear regression, t-test, Cohen's d.	2. Establish whether RM is more effective than RC in terms of improving behavioural and emotional difficulties.

Implementation and process evaluation

Research questions

The overarching objective of the implementation and process evaluation is to understand how the RM intervention is implemented and experienced by relevant stakeholder groups including the CYP, families and victims Remedi work with, as well the Remedi staff providing the intervention and professionals who refer into the intervention. The specific research questions are as follows:

1. Has the RM intervention been implemented as planned across Greater Manchester?
 - a. What has caused any variation from the planned implementation?
 - b. How and why does implementation vary across Greater Manchester districts?
2. How has the RM intervention been experienced by service users (CYP, families/carers, victims/harmed persons taking part in RJ)?
 - a. How does the experience of CYP vary between the RM and RC interventions?
3. How has the RM intervention been experienced by Remedi staff and referring organisations?
 - a. How and why does experience vary across Greater Manchester districts?

We will use these aspects of the study to assess the completeness and relevance of the Theory of Change already in place and any need for revisions, as well as the fidelity of the intervention and explore any reasons for a lack of fidelity.

Research methods

Interviews and focus groups will be used to gather the views of CYP, families, RJ victims, Remedi staff and other stakeholders (such as referring agencies) about their experience of the RC and RM intervention. This will be vital to understanding how the intervention has been experienced by those receiving it, how its different parts have interacted and any unintended consequences.

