## Introduction

The aim of this study is to evaluate whether a restorative mentoring programme for children and young people (CYP) is useful as a means of diversion from the criminal justice system. The new programme, termed Restorative Mentoring (RM), is compared to an alternative, light touch mentoring scheme termed Restorative Choices (RC). The RC scheme can be seen as a “basic” option, as it is similar to other typical programmes offered in the region. Both RM and RC are delivered by Remedi. Both interventions are described in the study protocol and in the pilot study report. CYP are referred to Remedi by the Greater Manchester Police and by Youth Justice Services.

The trial will be a two-armed individually randomised controlled trial. It will include an impact and a process and implementation evaluation. Upon referral to Remedi, eligible CYP will be randomly assigned to receive restorative mentoring (RM, the treatment group) or restorative choices training (RC, the control group) on a 1:1 basis. The primary outcome of interest in this study will be contact with police, where a CYP is a suspect including arrests and charges but also being linked to offences on which no further action is taken. The secondary outcomes will be the CYP's emotional and behavioural difficulties (as assessed by the Strengths and Difficulties Questionnaire) and their self-reported delinquency (as reported in the Self-Report Delinquency Scale (SRDS)). The process and implementation evaluation will consider the delivery of the Remedi interventions and the experience of them by all relevant groups. This design is considered by the research team to be the most appropriate to understand how the RM intervention operates and to assess its impact.

This design was used during a one-year pilot trial. No amendments have been made to the intervention or the study design as a result of this trial however the study did provide learning regarding the implementation of the study protocol which will support the current study.

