## Design overview

Please ensure all details are in line with the latest version of the protocol.

Trial design, including number of arms		Two-arm Randomised Control Study
Unit of randomisation		Individual CYP
Primary outcome	variable	The primary outcome of interest in this study will be contact with the police, as perpetrators, victims or missing person episodes.
	measure (instrument, scale, source)	Police contact data will be taken from Greater Manchester Police administrative records. Police contact data is a count variable starting at 0. These data will be collected one month before the trial ends. Data will be taken for a period 1 year prior to the recruitment date and 3 months after delivery ends for all CYP.
Secondary outcome(s)	variable(s)	
The secondary outcomes will be the CYP's emotional and behavioural difficulties and self-reported delinquency. Emotional and behavioural difficulties are measured by the following three variables:
 
 
1) Internalizing score
 
2) Externalizing score
 
3) Total difficulties
 
 
Self-reported delinquency is measured by:
 
 
4) Variety of delinquency
 
5) Volume of delinquency
 

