### Primary outcome analysis

The aim of the analysis is to answer the research question: did the Restorative Mentoring intervention (treatment) reduce post-treatment contact with the police compared to the Restorative Choices intervention (control)?

The primary outcome for this study is contact with the police, defined as the number of times the CYP appear in the police data as perpetrators, victims or for missing person episodes. These data will be taken from Greater Manchester Police administrative records.

Contact with the police is a discrete count variable starting at 0. These data will be collected one month before the trial ends, for a period 1 year prior to the recruitment date and for 3 months after completion of the intervention for all CYP.

It should be noted that the primary outcome, which is police contact with the CYP, is susceptible to biases in reporting and recording of crimes. These biases may stem from a number of factors, including characteristics of both the victim and the offender, such as ethnicity and gender. Nevertheless, we anticipate that the RCT design remains robust to these biases, as randomisation into the treatment and control groups is conducted independently of the police's reporting and recording of crimes.

There are two ways of analysing the data, depending on the distribution assumed for the dependent variable, which is total police contacts. As a discrete count random variable, it may be assumed to follow a Poisson or Negative Binomial distribution. However, if the mean of that distribution is far from 0, the Poisson and Negative Binomial distributions may be approximated by the continuous normal distribution. It is not clear a priori which distribution will be the better approximation, and therefore we consider below both scenarios. In any case, we do not expect major differences; the issue of whether a variable should be treated as continuous or discrete has received much attention in the randomized control trial literature and the main finding is that unless the outcome is binary or it is a "time to a first event", information will not be lost when treating a count variable as a continuous one, see, e.g. Herbison et al. (2015).

For the analysis, the headline estimate will be derived from an intention to treat effect (ITT), denoted by  $\beta$  in the regression:

$$g[E(Y_i|T_i)] = \alpha + \beta T_i,$$

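### The SAP Introduction gives a suspect-only primary outcome against a composite everywhere else; the protocol names two source systems and leaves the provider's extraction of the data unblinded on paper

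*SAP*

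**What the plan says.** **Definition.** The SAP Introduction says the primary outcome is "contact with police, where a CYP is a suspect including arrests and charges but also being linked to offences", whether or not the police act on them. Victim and missing-person contacts are not mentioned. The SAP's Primary outcome analysis section has a different variable, "defined as the number of times the CYP appear in the police data as perpetrators, victims or for missing person episodes". The SAP cover table and Design overview agree with that section ("contact with the police, as perpetrators, victims or missing person episodes"). So does the protocol in its cover table, Study rationale, Table 2, Outcome measures and Table 4. Under Primary outcome the protocol defends the broad count: the children were expected to have had little police contact, and "relying only on subsequent arrests and proven offending risked minimising their further contact with the police".

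**Source.** Protocol Table 1, Step 9, says "police administrative data are collected from the Police National Computer via GMP". The protocol's Primary outcome section says "This will be measured using police administrative data from Greater Manchester Police (COGNOS system"). The SAP refers only to GMP administrative records.

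**Extraction.** The protocol's Participants section says "The police administrative data will be collected by appropriately authorised Remedi staff that will be given access to a police computer". Table 4 describes the same step as "Provision of administrative data by Greater Manchester Police". Remedi delivers both arms, and under Randomisation its administrators contact the University to receive each allocation. That section says the mentor taking follow-up questionnaires will not know the arm. It says nothing of the kind about whoever extracts police records. Footnote 8 says the evaluators would create a rule so that repeat arrests for one offence count once.

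**The concern.** A suspect count and a composite of perpetrator, victim and missing-person contacts are different endpoints, with different means and, in general, different treatment ratios. When both appear in current SAP text, a report could headline either and point to the plan.

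This count carries the trial. It is the only outcome that is not self-reported. The SAP calls the secondary analysis exploratory, with about 148 end-point questionnaires expected from 352 children.

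The source matters for the same reason: if a named system lacks victim or missing-person records, the composite cannot be built from it. Extraction matters because the person selecting records works for the organisation delivering both arms. The SAP argues that randomisation protects against biased police recording, since allocation is independent of what the police record. That argument does not reach the selection or coding of records after randomisation by someone who may know the arm.

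**Working it through.** **1. The texts side by side**

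| Place | Contacts counted |
|---|---|
| SAP Introduction | suspect, including no-further-action links |
| SAP cover table, Design overview, Primary outcome analysis | perpetrator, victim, missing |
| Protocol cover table, Study rationale, Table 2, Outcome measures, Table 4 | perpetrator, victim, missing |

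One sentence stands against all the rest. It is body text of SAP v1.3 (6/2/2024), not a change log. Protocol v1.5 (30/4/2024) was revised to agree with the SAP and uses the composite throughout, so that revision did not remove the conflict.

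**2. The plan's own sample sizes**

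For d = 0.3, two-sided alpha 0.05 and 80% power: n per arm = 2(1.960 + 0.842)²/0.3² = 174.4, so 175 per arm and 350 in total. The stated 352 reproduces (power 0.804 at 176 per arm).

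For the count scale the SAP gives 322 in total, from a ratio of 1.22 and a pilot control mean of 1.8. A two-sided Poisson calculation gives n per arm = (1.960 + 0.842)² × (1/1.8 + 1/2.196)/(ln 1.22)² = 200.7, so 402 in total. A one-sided one gives 318. That discrepancy is a separate matter and nothing here rests on it. What matters here is that SAP footnote 2 does not say which definition the 1.8 was counted under.

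**3. Illustration: what the definition does to the ratio**

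The documents give no split by contact type, so the suspect share s is assumed, over 40% to 80%. Take a suspect-contact ratio of 1/1.22 = 0.82 and no effect on other contacts. The composite ratio is s × 0.82 + (1 − s); the mean cancels.

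| Suspect share s | Suspect-only ratio | Composite ratio |
|---|---|---|
| 80% | 0.82 | 0.86 |
| 60% | 0.82 | 0.89 |
| 50% | 0.82 | 0.91 |
| 40% | 0.82 | 0.93 |

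**4. Illustration: what it does to the power basis**

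If 1.8 is the all-contact mean, the suspect-only mean is 1.8 × 0.8 = 1.44 down to 1.8 × 0.4 = 0.72. Two-sided Poisson power with 176 per arm is Φ(ln 1.22/se − 1.96), where se² = (1/μ + 1/(1.22μ))/176.

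| Control mean μ | Power for a ratio of 1.22 |
|---|---|
| 1.8 | 0.75 |
| 1.44 | 0.65 |
| 0.72 | 0.38 |

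If instead 1.8 was a suspect-only mean, the composite mean would be 1.8/0.8 = 2.25 up to 1.8/0.4 = 4.5, and power for a given ratio would be higher. These figures assume no overdispersion; with it, power is lower.

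**5. Source and extraction**

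Step 9 and the Primary outcome section name different systems, and neither document says that either system holds all three record types. No section states whether the extractor knows allocation. That they may is an inference from three facts: Remedi delivers both arms, its administrators receive allocations, and blinding is stated for the follow-up questionnaires but not for this step.

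**The case against.** The strongest reply is that the endpoint is not in doubt. The conflict is one introductory sentence; the operative section defines the composite, the protocol gives a reason for it, and the later protocol version uses it throughout. That stands: a reader might infer that the endpoint is undecided, and the documents do not support this. They show an inconsistency with an evident intention behind it.

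Other strong readings also fail.

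- A reader might infer that mentoring several times a week would push victim or missing-person reports up while offending falls. The follow-up in the SAP's Primary outcome analysis starts at completion, when that contact has ended, and nothing in the documents shows the components moving in opposite directions.
- A reader might take Participants and Table 4 as contradicting each other on who supplies the data. Access to a police computer can be how GMP provides them.
- A reader might conclude that extraction is known to be unblinded. The protocol says authorised staff, not mentors; footnote 8 foresees a rule set by the evaluators; and the protocol plans cross-checks of linked data and an independent audit. These checks blind nobody, but they lessen the concern.

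What remains is the contradictory sentence, the two system names and the missing statement on blinding.

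**Conclusion.** The point holds as an inconsistency in the primary endpoint and its source, together with an unaddressed risk of ascertainment bias at extraction. It should be fixed, but it is not a fatal flaw, because the intended composite can be recovered from the rest of both documents. A pre-specified primary outcome should still not have to be recovered by inference.

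Its effect on the headline cannot be calculated from the documents. On the assumed shares of 80% to 40%, a suspect-only ratio of 0.82 corresponds to a composite ratio of 0.86 to 0.93. This rests on the assumed split, on no effect on victim and missing-person contacts, and on borrowing 1/1.22 from the SAP's count-scale effect. It shows that the definition matters, not what the trial will find.

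**What to change.** 1. Replace the SAP Introduction sentence with the definition in Primary outcome analysis. In SAP footnote 2, state under which definition the pilot mean of 1.8 was counted.
2. In protocol Table 1 Step 9, the protocol's Primary outcome section and the SAP, name one source, or one stated set of sources, that holds perpetrator, victim and missing-person records.
3. Report the three component counts as supporting analyses from the same extract.
4. Have the extractor export every record for each child, without selection or counting, from 1 year before recruitment to the extraction date. The University of Birmingham then applies the repeat-arrest rule and the follow-up window with a script fixed before allocation is merged.
5. State in the report that Remedi staff made the extract and may have known allocation.

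Withholding the arm from the extraction list would not be enough. It does not blind staff who may already know allocation, and a study ID alone cannot locate a police record. The follow-up window also needs completion dates, which can reveal the arm because RM lasts about 12 weeks and RC at most four. Hence the full export and the pre-fixed script, which leave no case-by-case choices to either party.

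The cost is a few wording changes, one script and three extra count tables. The protocol timeline has GMP data collected by 6 June 2025, so the changes should be made before then.
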